#### 9.2.2 Serious adverse events (SAEs)

A serious adverse event is any untoward medical occurrence or effect that

- results in death;
- is life threatening (at the time of the event);
- requires hospitalisation or prolongation of existing inpatients' hospitalisation;
- results in persistent or significant disability or incapacity;
- is a congenital anomaly or birth defect; or
- any other important medical event that did not result in any of the outcomes listed above due to medical or surgical intervention but could have been based upon appropriate judgement by the investigator.

An elective hospital admission will not be considered as a serious adverse event.

Given the observational design of this study, with only additional diagnostic data collection, the study will follow the recommendations of observational studies with additional diagnostic investigations. Only serious adverse events suspected to be related to study participation will be reported individually to the accredited METC within 7 -15 days of first knowledge.

The sponsor will report the SAEs through the web portal *ToetsingOnline* to the accredited METC that approved the protocol, within 7 days of first knowledge for SAEs that result in death or are life threatening followed by a period of maximum of 8 days to complete the initial preliminary report. All other SAEs will be reported within a period of maximum 15 days after the sponsor has first knowledge of the serious adverse events.

#### **9.2.3 Suspected unexpected serious adverse reactions (SUSARs)**

Not applicable.

### **9.3 Annual safety report**

Not applicable.

### **9.4 Follow-up of adverse events**

All AEs will be followed until they have abated, or until a stable situation has been reached. Depending on the event, follow up may require additional tests or medical procedures as indicated, and/or referral to the general physician or a medical specialist. SAEs need to be reported till end of study within the Netherlands, as defined in the protocol.

### **9.5 Data Safety Monitoring Board (DSMB) / Safety Committee**

In view of the observational design of the study, a data safety monitoring board or safety committee is not established.

## 10. STATISTICAL ANALYSIS

Categorical data will be presented as numbers (percentages) and compared using Chi-square test or Fisher's exact test. Continuous data will be assessed for normal distribution and presented as means  $\pm$  standard deviations or medians (interquartile ranges) whichever appropriate. Comparisons will be performed using the Student's t-test or Mann-Whitney U test, whichever appropriate.

For each patient studied, circulatory arrest data (case data) and non-circulatory arrest data (control data) will be collected. The data obtained will be analysed and used for algorithm development at regular intervals: after inclusion of the first 50 patients with at least one circulatory arrest and afterwards after inclusions of another 50 patients. This enables improvement and refinement of the initial algorithm to gain optimal performance. The first iteration provides a first version of the diagnostic algorithm. The second and third iteration will be used to optimize the algorithm. The fourth iteration will be used as final evaluation of the performance of the algorithm (internal validation). All non-circulatory arrest data will be analyzed for false positive circulatory arrest alarms.

As the algorithm will primarily be developed and validated on non-physiologic circulatory arrest induction using rapid ventricular pacing with aortic balloon inflation during transcatheter aortic valve implantation, a second (external) validation will be performed on data of patients with induced shockable cardiac arrest (i.e. induction of ventricular fibrillation or tachycardias). This most closely resembles clinical sudden cardiac arrest. The final cohort of 50 inclusions with at least one induced event, consisting only of patients who underwent VT ablation or VF induction after s-ICD implantation, will be used for this analysis.

The performance of the PPG-based algorithm will be assessed by calculating the sensitivity, specificity, and positive predictive value with 95% confidence intervals. The specificity is reported based on 1-minute intervals of pulsatile PPG signal correctly identified as non-circulatory arrest. Reporting will follow the recommendations of the STARD guidelines for studies on diagnostic accuracy. Statistical analyses will be performed using SPSS (IBM, Armonk, USA).

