## SUMMARY

**Rationale:** Out-of-hospital cardiac arrest (OHCA) is a leading cause of global mortality. Delays to initiation of cardiopulmonary resuscitation (CPR) should be as short as possible to achieve the highest survival chance. To reduce treatment delays automated cardiac arrest detection and call for help would be ideal. Photoplethysmography (PPG) is an optical technique often used in sport/smartwatches to monitor heart rhythm at the skin and based on previous studies it seems to have potential to detect circulatory arrest.

**Objective:** To study photoplethysmography signals during 1) induced circulatory arrest; 2) cardiac rhythms without circulatory arrest, and to construct a PPG-based algorithm for circulatory arrest detection.

**Study design:** Prospective multicenter observational study.

**Study population:** 1) Patients scheduled for defibrillation testing after (subcutaneous) implantable cardioverter defibrillator (ICD) implantation; 2) Patients undergoing transcatheter aortic valve replacement (TAVR) with intended rapid ventricular pacing; 3) Patients undergoing ventricular tachycardia ablation.

**Intervention:** Patients will be equipped with a wristband with a PPG-sensor to record PPG signals during hospital stay including during induced circulatory arrests. The circulatory arrest inductions are part of routine practice during above-described procedures and are not a study-related intervention. In case this is not routine practice, an arterial line will be inserted as reference standard for circulatory arrest.

**Main study parameters/endpoints:** Primary endpoints: Sensitivity for circulatory arrest and false positive circulatory arrest alarms.. Secondary endpoints: Positive predictive value for circulatory arrest, Specificity for detection of pulsatile PPG signal, PPG-signal characteristics.

**Nature and extent of the burden and risks associated with participation, benefit and group relatedness:** Given the observational nature of this study and the non-invasive comfortable wristband used for PPG signal recording, the medical risk associated with study participation is negligible. Insertion of an arterial line may carry small risks as outlined in this protocol.

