## **8. METHODS**

### **8.1 Study parameters/endpoints**

#### **8.1.1 Main study parameter/endpoint**

- Sensitivity of the developed algorithm for circulatory arrest detection and false positive circulatory arrest alarms.

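### Section 10 applies the primary false-alarm analysis to all non-arrest recordings, including those used to build the algorithm, and never says that the held-out figure is the primary one

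*Protocol*

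**What the plan says.** The Summary gives the endpoint pair as "Primary endpoints: Sensitivity for circulatory arrest and false positive circulatory arrest alarms", and Section 8.1.1 repeats it: "Sensitivity of the developed algorithm for circulatory arrest detection and false positive circulatory arrest alarms". In Section 2, the third primary objective explains performance, in brackets, as these same two quantities.

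Section 10 then fixes how the data are used:

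- Each patient contributes both kinds of data: "For each patient studied, circulatory arrest data (case data) and non-circulatory arrest data (control data) will be collected".
- Both feed the algorithm: "The data obtained will be analysed and used for algorithm development at regular intervals".
- The steps come "after inclusion of the first 50 patients with at least one circulatory arrest and afterwards after inclusions of another 50 patients".
- Building comes first: "The first iteration provides a first version of the diagnostic algorithm".
- Tuning follows: "The second and third iteration will be used to optimize the algorithm".
- Iteration 4 is set aside as the final evaluation of performance, which the Protocol calls internal validation.
- The next sentence reads: "All non-circulatory arrest data will be analyzed for false positive circulatory arrest alarms".

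The following paragraph adds an external validation in a final cohort of 50 patients with an induced event, all from VT ablation or s-ICD testing. Section 4.4 allows up to 80 additional patients and says that recordings from patients without an induced arrest join the non-arrest data. It assigns those patients to no iteration. The Protocol mentions neither cross-validation nor a correction for optimism, and it does not say which false-alarm figure is the primary one.

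**The concern.** An algorithm scored on the recordings used to build and tune it usually looks better than it will on new patients. The Protocol recognises this by holding back the fourth iteration and the final cohort. The sentence on non-arrest data carries no such limit, so a reader who follows it literally would count alarms in development and held-out recordings together and report one rate.

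This matters because detection algorithms generally trade missed arrests against false alarms. If sensitivity were quoted from held-out patients and false alarms from pooled data, a tuning step that suppresses alarms would show its cost in new patients and its benefit largely in the patients used to choose it. Positive predictive value and specificity would be affected as well if they were computed on the same pooled data. Section 10 does not say which data they use. The stated aim of the wider project is a wristband that calls the emergency services, so the false-alarm rate is not a side result.

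**Working it through.** **The plan's own figure.** Section 4.4 gives a precision only for sensitivity: 95% with 200 events, ±3%. It reproduces: 1.96 × √(0.95 × 0.05 / 200) = 0.0302. No figure is given for false alarms, so this neither supports nor weakens the point.

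**Development patients.** Iteration 1 builds (50) and iterations 2 and 3 refine (2 × 50), so 50 + 100 = 150 patients.

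**Share of the non-arrest data.** The share is f = 150 / total patients. It assumes equal non-arrest recording time per patient and that no patient without an arrest was used in development.

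- Iterations 1 to 4: 150/200 = 75%.
- With the final cohort: 150/250 = 60%.
- Planned enrolment (Section 4.4): 150/276 = 54%.
- Maximum enrolment: 150/(276 + 80) = 150/356 = 42%.

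The 250 is the sum of the groups in Section 10. The event rates in Section 4.4 give 200 + 20 + 56/3 ≈ 239 patients with an event, and 150/239 = 63% lies inside the same range. The last two shares are the closest to the literal wording, because patients without an arrest also supply non-arrest data.

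**Effect on the pooled rate.** Let r be the false-alarm rate in development data divided by the rate in unseen data. Then pooled rate / true rate = f × r + (1 − f). The value of r is not in the Protocol; those below are assumed.

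| r (assumed) | f = 75% | f = 60% | f = 54% | f = 42% |
|---|---|---|---|---|
| 0.9 | 0.93 | 0.94 | 0.95 | 0.96 |
| 0.75 | 0.81 | 0.85 | 0.86 | 0.89 |
| 0.5 | 0.63 | 0.70 | 0.73 | 0.79 |

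For example, at f = 75% and r = 0.5: 0.75 × 0.5 + 0.25 = 0.625. Over this grid the pooled rate understates the true rate by about 4% to 38%. With r = 1 there is no bias.

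**The case against.** The best reply is that a held-out false-alarm evaluation is already implied. Section 2 explains performance as sensitivity and false positive alarms, and Section 10 reserves iteration 4 for evaluating performance. Read together, iteration 4 covers both halves of the endpoint. This stands. A reader might infer that the Protocol evaluates only sensitivity on new patients and false alarms only on everything, so that the two primary figures can never describe one operating point. The documents do not say that, because Section 10 does not tie sensitivity alone to iteration 4.

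The sentence also has milder readings. It follows directly on the one about iteration 4 and may mean all non-arrest data in that evaluation. It may signal that patients without an induced arrest count too, as Section 4.4 says. It may serve the secondary objective of finding sources of false alarms, for which screening every recording is legitimate. Each reading is possible, but the wording states none of them, and the unrestricted scope conflicts with a held-out evaluation unless one figure is named as primary. An analysis plan that is not shown might narrow the set. The Protocol nevertheless states the scope itself.

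The mechanism and the size are also open to challenge. The Protocol does not say that tuning targets false alarms, only that the algorithm is optimised. Exposure to false alarms accrues by recording time rather than by patient, and times may differ between TAVR, ICD and VT-ablation procedures. These objections limit what can be said about size; they do not remove the expected direction.

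**Conclusion.** The point holds as a conflict inside Section 10. Iteration 4 and the final cohort are reserved for evaluation, yet the false-alarm sentence covers all non-arrest data, and no passage says which figure is primary. Followed literally, the primary false-alarm result would include recordings from about 150 development patients, 42% to 75% of the total depending on who is counted, with equal recording time per patient assumed. If patients without an arrest were also used in development, the shares based on total enrolment would be higher.

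The pooled rate is expected to be optimistic, by an unknown amount. The range of about 63% to 96% of the true rate rests on an assumed ratio of 0.5 to 0.9. A reader might infer that the reported rate will be roughly half the true one; the documents support no such number, and the bias could be small. Nor do they show that specificity and positive predictive value are affected, since their data set is not named.

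**What to change.** Add to Section 10, after the sentence on non-arrest data, wording to this effect:

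*The primary false-positive analysis uses only non-arrest recordings from patients not used for development, namely those of iteration 4, with the final validation cohort reported alongside. It uses the same locked algorithm version as the sensitivity analysis. Recordings from patients without an induced arrest count as held-out only if those patients played no part in development. False alarms in iterations 1 to 3, and in all data pooled, are reported separately as descriptive results, including for identifying sources of false alarms.*

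No new patients or measurements are needed. The cost is less recording time for the primary false-alarm estimate and hence a wider interval. Using 50 patients instead of the 200 in iterations 1 to 4 widens it by roughly √(200/50) = 2, if patients contribute equal time and the rate is the same. The pooled figure remains available as a descriptive result. If iteration 4 was what the sentence meant all along, the addition only makes that explicit.

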## 2. OBJECTIVES

Primary Objectives:

- 1) To study PPG signal characteristics in relation to circulatory arrest in patients with induced circulatory arrest.
- 2) To construct a PPG-based algorithm for detection of circulatory arrest based on induced circulatory arrest data in patients.
- 3) To study the performance (sensitivity and false positive alarms) of the developed PPG-based algorithm for detection of circulatory arrest in patients with induced circulatory arrests.

Secondary Objective(s):

- To study the positive predictive value of the developed algorithm for circulatory arrest detection.
- To study the specificity of the developed circulatory arrest detection algorithm.
  
- To identify potential sources of false positive alarms for circulatory arrests.
- To study PPG signal characteristics in relation to hemodynamically stable cardiac arrhythmias.
- To study PPG signal characteristics in relation to hemodynamically unstable cardiac arrhythmias.
- To study PPG signal characteristics prior to and after TAVR procedure to assess the impact of aortic stenosis and/or regurgitation on the PPG signal.
- To study PPG signal characteristics in patients with and without systemic hypertension.
- To study PPG signal characteristics in relation to left ventricular ejection fraction in patients without relevant valvular lesions.

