### 4.4 Sample size calculation

Targeting a desired sensitivity of 95%, 200 true events allow estimation of sensitivity with precision (expressed as expected width of the 95% confidence interval) of +/- 3%, which is considered adequate. As for specificity, a substantially larger number of “non-events” can be sampled, precision for estimating specificity will be larger.

In this study, we will primarily collect data of induced circulatory arrest, obtained during controlled settings with appropriate reference standards (ECG and (invasive) blood pressure measurements). To collect a sufficient amount of PPG data with true events, the

sample size will be 276 patients consisting of an estimated number of n=200 TAVR-patients (event rate 1/1), n=20 ICD-patients (event rate 1/1) and n=56 VT-ablation patients (event rate 1/3). In case ventricular fibrillation induction or rapid ventricular pacing is not performed or does not result in complete circulatory arrest (as determined on (invasive) blood pressure measurements), the number of patients included will be increased to guarantee the anticipated number of true events, with a maximum of 80 additional patients. Data of the patients without induced circulatory arrest will be used as non-cardiac arrest data.

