### 8.3.2 VT ablation

During VT ablation, hemodynamically unstable VT/VF is induced in about 1/3 of patients. Patients will wear the wristband during the entire procedure. This enables collection of PPG data in settings with and without circulatory arrest. In case an arterial line is not inserted for clinical purposes, patients will be asked consent to do so. The presence of circulatory arrest is confirmed by simultaneously recorded invasive blood pressure measurements and ECG recordings. Therefore, in patients in whom this is not standard of care, consent will be asked to insert an arterial line into the radial artery to measure blood pressure during ventricular fibrillation to confirm complete circulatory arrest. ECG and invasive blood pressure measurements will be digitally stored and collected. Available echocardiographic data will be collected. The wristband is removed after the procedure. Activities are described in Table 1.

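### The external validation admits only patients with an induced event, so event-free VT-ablation patients have no stated place in its specificity, false-alarm and PPV estimates

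*Protocol*

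**What the plan says.** Section 10 announces that "a second (external) validation will be performed on data of patients with induced shockable cardiac arrest", because rapid pacing with balloon inflation during TAVR is not a physiological arrest. The cohort for it is "The final cohort of 50 inclusions with at least one induced event, consisting only of patients who underwent VT ablation or VF induction after s-ICD". The same section names sensitivity, specificity and PPV as the performance measures and counts specificity in 1-minute pulsatile intervals. It also says that each patient contributes both arrest and non-arrest data, and that all non-arrest data will be examined for false alarms.

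Section 4.4 plans "n=20 ICD-patients (event rate 1/1") and "n=56 VT-ablation patients (event rate 1/3"). Section 8.3.2 on VT ablation agrees: "During VT ablation, hemodynamically unstable VT/VF is induced in about 1/3 of patients". On patients who have no arrest, Section 4.4 says: "Data of the patients without induced circulatory arrest will be used as non-cardiac arrest data".

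False alarms are part of the main endpoint (Section 8.1.1). Specificity and PPV are secondary (Section 8.1.2).

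**The concern.** Entry to the external cohort depends on the target condition having occurred. For sensitivity that is the right denominator. For the measures that describe behaviour in the absence of arrest, it removes the ICD and VT-ablation patients in whom every alarm is false by definition. These patients may include some with an induced tachycardia that keeps a pulse, a setting that Section 2 lists for study in its own right.

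Section 10 regards induced shockable arrest as the closest model of clinical sudden cardiac arrest, so readers will give most weight to this validation. As written, its control data come only from event patients, and every patient counted brings at least one true event into the PPV. Recordings from event-free patients, already made and potentially held out from development, go only into a pooled false-alarm count. The protocol does not split that count into development and evaluation data.

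**Working it through.** **The plan's own figures.** Half-width for sensitivity: 1.96 × √(0.95 × 0.05 / 200) = 0.0302, which agrees with the stated ±3%. Total: 200 + 20 + 56 = 276, as stated.

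**Who falls outside the external cohort** (Section 4.4 numbers and rates):
- ICD and VT-ablation patients: 20 + 56 = 76.
- Expected with an event: 20 + 56/3 = 38.7.
- Expected without an event: 56 × 2/3 = 37.3, or 37.3/76 = 49% of the two groups.

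**Planned numbers against the cohort of 50.** The planned numbers give 38.7 event patients, not 50. If all 20 ICD patients have an event, the remaining 30 need 30 × 3 = 90 VT-ablation patients. That makes 110 patients in all, of whom 60 have no event. Both cases are shown below.

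**PPV.** With E event patients, N patients scored, sensitivity S and f false alarms per patient:

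PPV = S·E / (S·E + f·N)

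Assumptions: S = 0.95 (the protocol's target), one event per event patient, and the same f in event and event-free patients. The protocol gives no f, so a range is shown.

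| f (assumed) | Event patients only (N = E) | All 76 (E = 38.7) | All 110 (E = 50) |
|---|---|---|---|
| 0.01 | 99.0% | 98.0% | 97.7% |
| 0.05 | 95.0% | 90.6% | 89.6% |
| 0.10 | 90.5% | 82.9% | 81.2% |
| 0.50 | 65.5% | 49.2% | 46.3% |

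At f = 0.10: 0.95/1.05 = 90.5%; 36.73/(36.73 + 7.6) = 82.9%; 47.5/(47.5 + 11) = 81.2%. The sizes depend on the assumptions. The direction does not: any false alarm in an event-free patient adds to the denominator and nothing to the numerator.

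**Precision of specificity.** Assumptions: true specificity 99%, 60 pulsatile minutes per patient, independent minutes. Half-width = 1.96 × √(0.99 × 0.01 / (60 × patients)):
- Planned numbers: 0.40 percentage points with 38.7 event patients, 0.29 with all 76. The ratio is √(38.7/76) = 0.71.
- Cohort filled to 50 events: 0.36 points with 50 patients, 0.24 with all 110. The ratio is √(50/110) = 0.67.

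Clustering of minutes within patients would widen every one of these intervals. On these assumptions, the gain from adding event-free patients is real but small in absolute terms.

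**The case against.** The strongest reply is that event-free patients are not lost. Sections 4.4 and 10 keep their recordings as non-arrest data and send all such data to the false-alarm analysis. Because each patient supplies control minutes, specificity and false alarms also remain estimable inside the event-only cohort. Both points stand. A reader might infer that these patients cannot be scored, or that the algorithm goes untested in them; the documents do not support that. What the reply leaves open is that the false-alarm sentence covers all data, including data used to build the algorithm, and does not say that event-free patients contribute to the external validation.

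A second reply is that PPV is artificial under any induced event rate, whether from event patients alone or from all ICD and VT-ablation patients. That also stands. Neither figure transfers to daily life, and the wider denominator only avoids having a true event in every patient counted. The second validation was added chiefly to test transfer to shockable arrest, which is mainly a question of sensitivity.

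Two further inferences are tempting and should not be drawn:
- Objective 3 in Section 2 speaks of performance "for detection of circulatory arrest in patients with induced circulatory arrests". This could be read as restricting false alarms to event patients, in conflict with Section 10. It reads more naturally as a description of the study, in line with its title and base population.
- The iteration rule, "after inclusion of the first 50 patients with at least one circulatory arrest and afterwards after inclusions of another 50 patients", could be read as dropping the event requirement after the first batch. The later wording is most simply shorthand for the earlier.

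**Conclusion.** The point holds in a limited form. The external cohort is selected on the event. By the protocol's own rate, about 37 of 56 VT-ablation patients fall outside it, and the text does not bring their control data back in. The consequences are a narrower range of controls, modestly wider intervals for specificity, and a PPV that is higher by construction. The PPV difference is about 8 points at planned numbers (90.5% against 82.9%), or about 9 points if enrolment runs to 50 event patients (90.5% against 81.2%). Both differences assume 0.1 false alarms per patient, 95% sensitivity, one event per event patient and equal false-alarm rates. At 0.01 false alarms per patient the difference is only about 1 point. Sensitivity in the second validation is unaffected.

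**What to change.** In Section 10, give the second validation two denominators:
- Sensitivity: patients with an induced event, as now.
- Specificity and false alarms: all VT-ablation and s-ICD patients belonging to the external cohort, with or without an event. Report PPV on the same set, stating that its prevalence is the procedural induction rate and not that of clinical use.

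Add that event-free ICD and VT-ablation patients are assigned to the held-out cohort by procedure group. Enrolment date should not be the rule: it would move such patients enrolled during the first three iterations into development, and shrink a cohort whose planned numbers already give only 38.7 event patients against 50. Report false alarms on evaluation data separately from those on data used to develop the algorithm.

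The cost is small. No extra patients or procedures are needed, because VT-ablation patients already wear the wristband for the whole procedure (Section 8.3.2, VT ablation). The downside is slightly more analysis work and possibly a less favourable PPV or specificity.

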# **Photoplethysmography to detect circulatory arrest: A study in patients with induced cardiac arrests**

## **- DETECT-1 -**

**(October 2023)**

### Protocol amendments:

Amendment 1 - June 2022: the maximum number of patients in whom no circulatory arrest was induced (no need for rapid ventricular pacing with aortic balloon dilatation during TAVR) that could be included was increased and it was better explained that the collected data is used as non-circulatory arrest data.

Amendment 2 - November 2022: the number of TAVR-patients to be included was increased, and number of s-ICD and VT ablation patients was decreased.

Amendment 3 – October 2023: removing extended data collection from the protocol, detailing the statistical analysis including addition of a subgroup for external validation.

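### The base sample yields about 39 ICD and VT-ablation event-patients for an external-validation cohort set at 50, and no rule withholds these patients from the development batches

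*Protocol*

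**What the plan says.** Protocol Section 10 describes five sets of 50 event-patients. The first four are successive batches, each closed when another 50 patients with at least one circulatory arrest have been included. The first produces the algorithm, the second and third refine it, and the fourth is the internal validation. The batches are defined by this count alone, with no restriction by procedure. The section says that development and validation rest *primarily* on TAVR pacing data, and for that reason adds an external validation on "The final cohort of 50 inclusions with at least one induced event, consisting only of patients who underwent VT ablation or VF induction" (the latter in s-ICD patients). It regards these arrests as the closest to clinical sudden cardiac arrest.

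Section 4.4 gives the numbers:

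- Precision basis: "Targeting a desired sensitivity of 95%, 200 true events allow estimation of sensitivity with precision", where precision is "expressed as expected width of the 95% confidence interval) of +/- 3" percentage points.
- Total and TAVR share: "sample size will be 276 patients consisting of an estimated number of n=200 TAVR-patients (event rate 1/1").
- The other two groups: "n=20 ICD-patients (event rate 1/1) and n=56 VT-ablation patients (event rate 1/3").
- Up to 80 further patients may be added when VF induction or rapid pacing is not done, or leaves the arrest incomplete, so that the expected count of true events is kept.

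Section 8.3.2 (VT ablation) repeats the rate: "hemodynamically unstable VT/VF is induced in about 1/3 of patients".

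The amendment list shows how the two sections may have drifted apart. Under Amendment 2 the "number of s-ICD and VT ablation patients was decreased", and the later Amendment 3 added the external-validation subgroup. The conflict itself lies between the current Section 4.4 and the current Section 10.

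**The concern.** Section 10 fixes the size of a cohort that may contain only ICD and VT-ablation patients, while Section 4.4 fixes how many such patients are planned and how often they have an event. The two do not match. This cohort is the only planned test of the finished algorithm restricted to arrests other than pacing-induced ones.

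The second issue is independence. If an ICD or VT patient included early counts towards one of the first four batches, that patient has either helped to shape the algorithm or already been used in the internal validation. Counting the same patient again in the external cohort would make the sensitivity there look better founded than it is. A shortfall against 50 adds pressure to do so.

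**Working it through.** **1. The plan's own figures reproduce.** The Wald half-width at 95% sensitivity with 200 events is 1.96 × √(0.95 × 0.05 / 200) = 0.0302, the stated 3 points. The groups add up: 200 + 20 + 56 = 276.

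**2. Event-patients expected for the external cohort.** Inputs from Section 4.4: 20 ICD at 1/1 and 56 VT at 1/3.

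20 × 1 + 56 × 1/3 = 20 + 18.67 = 38.67

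Against 50, the shortfall is 11.33, or 23%.

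**3. Chance of reaching 50 from the base sample.** If all 20 ICD patients have an event, at least 30 of 56 VT patients (54%) must have one too. Exact binomial tail P(X ≥ 30 | n = 56):

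| VT event rate | Expected ICD + VT event-patients | P(at least 50) |
|---|---|---|
| 1/3 (Section 4.4) | 38.7 | 0.0014 |
| 40% (assumed) | 42.4 | 0.027 |
| 50% (assumed) | 48.0 | 0.34 |

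**4. Total over all five sets.** Needed: 4 × 50 + 50 = 250. Expected: 200 + 20 + 18.67 = 238.67. The gap is again 11.33, because 200 TAVR patients at 1/1 exactly fill four batches of 50. The whole shortfall therefore falls on the ICD and VT groups.

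**5. What would fill the cohort on expectation.** VT patients needed: (50 − 20) / (1/3) = 90, which is 34 more than planned. Alternatively, about 12 more ICD patients (11.33 rounded up).

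**6. The 80-patient allowance.** All 80 as VT patients: 20 + (56 + 80)/3 = 65.3. All 80 in the planned mix: 38.67 × (276 + 80)/276 = 49.9. So it could close the gap. At the stated 1/1 rates for TAVR and ICD, however, its trigger is never met, and Section 4.4 does not link it to a cohort of 50.

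**7. Cost in precision.**

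| Event-patients | Wald half-width at 95% | Exact 95% CI |
|---|---|---|
| 50 | 6.0 points | 86.3–99.5% (48/50 detected) |
| 39 | 6.8 points | 82.7–99.4% (37/39 detected) |

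**8. Separation.** Section 10 admits a patient to a batch for having at least one circulatory arrest. An ICD or VT patient with an event meets that condition. The word *primarily* allows such patients into development, and no sentence withholds them.

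**The case against.** The strongest reply is that the intended design is clear enough. The 200 TAVR patients match four batches of 50, and the external cohort is described as final, external and limited to ICD and VT patients. The natural reading is TAVR batches first and a separate ICD/VT cohort afterwards. The group sizes are called estimates, and 80 more patients may be included. The loss from 50 to 39 is only 0.8 points of half-width, and the protocol sets no precision target for this cohort.

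Much of this stands, and it rules out several stronger readings that a reader might infer:

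- *That the cohort cannot be filled at all.* Step 6 shows that the allowance could fill it if it were directed there. The shortfall belongs to the base sample.
- *That contamination has occurred.* The protocol does not show this; it only fails to exclude it.
- *That only about 6 unused ICD/VT patients would remain.* The figure comes from 200 × 38.67/238.67 = 32.4 falling in the first four batches, leaving 6.3. It assumes even enrolment over time, and the protocol gives no enrolment order.
- *That 200, 238.7 and 250 are three conflicting totals.* The 200 is a count of true events for a precision statement, and a yield of 238.7 satisfies it. Only 238.7 against 250 is a mismatch.
- *That 38.7 is an upper limit because the 1/3 describes unstable VT/VF and not confirmed arrest.* Section 4.4 itself labels 1/3 the event rate, and an approximate rate may err either way.

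The natural reading does not remove the point. Even if every ICD and VT patient is reserved, about 39 are expected, not 50. An intention that has to be inferred is also not a rule that protects the independence of a validation set.

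**Conclusion.** The point holds in two parts. First, the stated external-validation size of 50 is not supported by the numbers in Section 4.4: about 39 event-patients are expected, a shortfall of about 11, with a probability near 0.001 of reaching 50. This rests on the stated group sizes and rates, on every ICD patient having an event, and on the allowance not being used for this cohort. Second, the separation of this cohort from iterations 1 to 4 is implied but not stated.

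The arithmetic shortfall alone costs little precision and does not touch the 200-event basis for the main sensitivity estimate. The separation gap matters more, because reuse of patients would undermine the claim of external validation, though the documents show it only as a possibility. Both should be settled before the external validation is run.

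**What to change.** In Section 10, define the external cohort as all available ICD and VT-ablation event-patients not used in iterations 1 to 4, with about 39 expected, and give the precision that this allows (half-width about 6.8 points at 95% sensitivity; exact interval about 83–99% if 37 of 39 are detected). State that ICD and VT patients are withheld from iterations 1 to 4. Report any who were already used before Amendment 3 separately, outside the external cohort. Then align the totals, so that Section 4.4 shows the event-patients expected for the four batches and for the external cohort, and Section 10 uses the same figures.

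The cost is a smaller stated validation size and little slack elsewhere. With ICD and VT patients withheld, four batches of 50 need an event in every one of the 200 planned TAVR patients, while Section 4.4 already foresees some without a complete arrest. The 80-patient allowance should therefore stay available for TAVR patients without arrest. Keeping the figure of 50 by drawing on that allowance for ICD and VT patients is arithmetically possible, but it would compete with this need.
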